### **Multi-center Studies**

In this multi-center clinical trial, to allow for center-specific effect sizes, center will serve as a random effect in all primary analyses comparing treatment arms. Model fitting problems from sparse data may be encountered since enrolment stopped early due to COVID-19. If that occurs, then network (US, Canada, UK, Australia) will serve as random effect. As exploratory analyses, results within center or network will be described.

## **Missing Data**

Adhering to the definition of the primary outcome as either death or a decline from baseline of >10 percentage points in percent predicted FVC, reached by week 52, all participants will be included in the ITT population. Outcomes involving repeated measurements will be analyzed using mixed models, accommodating varying amounts of follow-up data among participants. The statistical models allow for missing data, assuming they are missing at random. Even participants with only one post-baseline assessment can be included, and can therefore contribute to variance estimation. It is reasonable to assume that missing data due to COVID-19 center closures are missing at random. The statistical model assumes that participants who prematurely discontinue study participation would have behaved similarly to those who remained in the study. The mixed effect model for repeated measures analyses allows for form-level missing data, assuming they are missing at random. Item-level data for PROs will be handled according to the instructions provided by the instrument developer.

Sensitivity analyses using alternative assumptions will be conducted to investigate the potential effect of missing data on the results of the primary analysis. One such analysis will exclude participants with less than six months of follow-up. It is conceivable that one arm, such as the active drug arm, may have more early discontinuations and/or more missing data than the other arm. The extent of missing data will be reported overall and by treatment arm, and quantified for key primary and secondary endpoints, with a graphical representation. Reasons for treatment discontinuation and for study discontinuation will be reported. Because missing data arising from the temporary closure of centers due to the COVID-19 pandemic is assumed to be missing at random, treatment arm comparisons will be valid. Where covariates are missing, a value of 0 will be imputed, along with a missing-indicator variable for the covariate as an additional covariate in the regression model (White, Thompson, 2005).

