## **Study Methods**

### **General Study Design and Plan**

This parallel-group double-blind randomized longitudinal study was designed to assess the superiority of Pirfenidone versus placebo, over a 52-week follow-up period. Patients are randomized with equal probability to receive Pirfenidone or placebo. After the screening visit, randomization occurs at visit 2. The week 52 visit is visit 11. Adverse events are additionally queried by phone 28 days after visit 11.

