## **Study Assessments**

The schedule of all study assessments is in **Appendix A** of the protocol. Eligibility and randomization take place at Visit 2. Time windows for visits are below. There is an additional phone visit that occurs 28 days after the last study drug dose to assess vital status and adverse events.

Visit Number	Visit Week	Target Day of Visit	Visit Window
1	-8 to 0	-56 to 0	-56 to 0 days
2	0	1	0
3	1	7	± 2 days
4	2	14	± 2 days
5	4	28	± 1 week
6	8	56	± 1 week
7	13	91	± 2 weeks
8	19	133	± 1 week
9	26	182	± 2 weeks
10	39	273	± 2 weeks
11*	52	364	± 1 week

\* Visit 11 marks the end of the follow-up period. Protocol amendment V8 (US/CAN/AUS) /V10 (UK) extends the visit 11 window to ± 4 weeks due to COVID-19 laboratory closures.

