## **Primary and Secondary Endpoints and Relevant Variables**

*Composite endpoint of decline from baseline in percent predicted FVC of 10% or greater or death during study period.*

- FVC (percent predicted) at baseline
  - Last FVC (percent predicted) while on study
- Decline from baseline in percent predicted FVC is (last percent predicted FVC while on study) - (percent predicted FVC at baseline)
- Death (yes/no) while on study

*Decline from baseline in percent predicted FVC of 10% or greater during study period.*

- FVC (% predicted) at baseline
  - Last FVC (% predicted) while on study
- Decline from baseline in percent predicted FVC is (last percent predicted FVC while on study) - (percent predicted FVC at baseline)

*Frequency of progressive disease as defined by OMERACT: Relative decline from baseline in percent predicted FVC of  $\geq 10\%$ , or relative decline from baseline in percent predicted FVC  $\geq 5\%$  and  $< 10\%$ , and  $\geq 15\%$  relative decline from baseline in percent predicted DLCO (Khanna, Mittoo et al. 2015)*

- FVC (percent predicted) at baseline
  - Last FVC (percent predicted) while on study
- Relative decline from baseline in percent predicted FVC = [(Last FVC(percent predicted) – Baseline FVC (percent predicted))/Baseline FVC (percent predicted)]\*100
- DLCO (percent predicted) at baseline
  - Last DLCO (percent predicted) while on study

Relative decline in percent predicted DLCO = [(Last DLCO (percent predicted) – Baseline DLCO (percent predicted))/Baseline DLCO (percent predicted)]\*100

If DLCO (percent predicted) is missing, TLCO (percent predicted) will be substituted.

*Change from baseline over study period in FVC (L)*

- FVC (L) at baseline
- Last FVC (L) while on study

*Change from baseline over study period of percent predicted FVC*

- FVC (percent predicted) at baseline
- Last FVC (percent predicted) while on study

*Slope of percent predicted FVC over study period*

- All available percent predicted FVC measurements and dates while on study

*Slope of absolute FVC over study period*

- All available FVC measurements and dates while on study

*Time to decline of 10% or greater in percent predicted FVC at death over study period*

- Baseline percent predicted FVC and randomization date
- All measurements of percent predicted FVC while on study and date
- Death date, death indicator
- Last study visit date

*Proportion of participants with all-cause mortality*

- Death date present or absent

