## **Sensitivity Analyses**

To assess the robustness of the primary analysis of the primary endpoint, the following two sensitivity analyses will be performed. (1) The analysis of the primary composite endpoint will be repeated using the Per-Protocol population. (2) The analysis of the primary composite endpoint will be repeated using an adaptation of the Per-Protocol population where the lower threshold for medication compliance will be reduced from 80% to 65%.

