## **Coronavirus Disease 19 (COVID-19)**

The effect of COVID-19 on TRAIL1 will be investigated as follows: Protocol deviations due to COVID-19 will be presented and visits out of window due to COVID-19 will also be identified. Sensitivity analyses will be determined if necessary prior to database lock, and may include the following: Excluding all affected participants, using time-varying covariates to identify measurements taken during the affected period, increasing the duration of visit windows beyond those specified in the protocol, setting all data in a participant's affected period to missing and imputing values. (reference: Ongoing trials during COVID-19: Quantitative strategies and methodological aspects: Cytel, Inc. 2020.)

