## **Subject Disposition**

Please refer to the accompanying spreadsheet for forms and variable names (TRAIL1 endpoints and dataset variable names.xlsx, Subject Disposition tab.)

The consort diagram will be presented.

<http://www.consort-statement.org/consort-statement/flow-diagram>

The number of participants reaching the milestones in the trial will show the number screened, randomized, and reaching each visit, or study close, and the number dropped out and for what reasons (death, toxicity, treatment failure, withdrew consent). A crosstabulation will show the accrual by quarter and by network and center. A listing of participant discontinuation from study medication will be presented for all randomized participants. Frequency counts and percentages of all participants providing informed consent, randomized/enrolled, completing and discontinuing from the study and study treatment will be presented according to treatment arm and overall. A summary of discontinuations will also be presented by visit. The proportion who discontinued the study early will be compared using chi-square test in the ITT population. The proportion who stopped treatment early on each arm will be compared using chi-square test in the as-treated population.

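### The one missing-data sensitivity analysis that the SAP names can discard primary events already observed, and it does not test a departure from missing at random

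*SAP*

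**What the plan says.** The Missing Data section of the SAP makes a general commitment: "Sensitivity analyses using alternative assumptions will be conducted to investigate the potential effect of missing data on the results of the primary analysis". It then names a single method: "One such analysis will exclude participants with less than six months of follow-up". No exception is made for participants who died or who had already met the FVC criterion. The same section assumes that early leavers would have behaved like those who stayed, and it warns that one arm, for instance active drug, may have more early discontinuations or missing data.

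Two other SAP sections mention sensitivity analyses:
- **Sensitivity Analyses** says that "the following two sensitivity analyses will be performed". Both repeat the primary analysis in a per-protocol set, with lower compliance limits of 80% and 65%.
- **Coronavirus Disease 19 (COVID-19)** says "Sensitivity analyses will be determined if necessary prior to database lock, and may include the following". Imputation is among the options, but none is fixed.

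The primary endpoint has no minimum time on study. Its inputs in Primary and Secondary Endpoints and Relevant Variables are the last percent predicted FVC on study and "Death (yes/no) while on study".

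**The concern.** A missing-data check should vary what is assumed about outcomes nobody saw. This rule selects on length of follow-up, which is measured after randomization and can be cut short by the outcome itself. A death in month 3 is a known primary event. So is a withdrawal in month 4 with a last FVC 10 or more points down. Neither has a missing outcome, yet the rule as worded can remove both.

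If early events fall unevenly between the arms, the check will agree or disagree with the primary result for reasons unrelated to missing data, and a reader cannot tell which. Nor does leaving out the early leavers ask what would follow if their unseen Week-52 values were worse than those of similar participants who stayed. That is the question raised by the SAP's own warning about unequal missingness.

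**Working it through.** **1. What follow-up means.** The SAP gives no participant-level definition. Its other uses of the term concern elapsed study time: "over a 52-week follow-up period" in General Study Design and Plan, and "Visit 11 marks the end of the follow-up period" in Study Assessments. Subject Disposition reports "the number dropped out and for what reasons (death, toxicity, treatment failure, withdrew consent"), so death is listed among the reasons for dropping out. These passages favour reading it as time on study, but they do not settle the matter.

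**2. Whether an event can be observed before six months.** Yes. Protocol 7.2.2 schedules spirometry at Week 13 and again at the Early Termination Visit, which is meant for participants who withdraw consent in writing or receive a transplant. Participants who only stop study drug are asked to continue visits to Week 52 (Protocol 5.3.3) and are not the issue here.

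**3. The plan's own figure.** The claim rests on the text, not on a stated number. The design rates used below do reproduce the plan's sample size. With 0.32 versus 0.16, two-sided 5% alpha, 85% power and pooled variance, n per arm = [1.960·√(2·0.24·0.76) + 1.036·√(0.32·0.68 + 0.16·0.84)]² / 0.16² = 126.4. This rounds up to 127, or 254 in total, as in Protocol 10.2.1.

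**4. Illustration (all inputs assumed).** The SAP gives 123 randomized. I take 62 and 61 per arm with 20 and 10 events, close to the design rates, which come from an IPF trial.
- Difference: 20/62 − 10/61 = 32.3% − 16.4% = 15.9 points.
- SE: √(0.323·0.677/62 + 0.164·0.836/61) = 7.6 points.
- Odds ratio: (10/51)/(20/42) = 0.41.

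The documents give no RA-ILD death rate. At an assumed annual mortality m of 4% to 10%, deaths before six months number 123·(1 − (1 − m)^0.5), which is 2.5 to 6.3. I remove four early events. The arithmetic is the same for a death and for an early leaver with a qualifying FVC.

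| Removed (placebo/pirfenidone) | Remaining events | Difference | Shift | Odds ratio |
|---|---|---|---|---|
| 4/0 | 16/58 vs 10/61 | 11.2 | −4.7 | (10/51)/(16/42) = 0.51 |
| 3/1 | 17/59 vs 9/60 | 13.8 | −2.1 | (9/51)/(17/42) = 0.44 |
| 2/2 | 18/60 vs 8/59 | 16.4 | +0.6 | (8/51)/(18/42) = 0.37 |
| 1/3 | 19/61 vs 7/58 | 19.1 | +3.2 | (7/51)/(19/42) = 0.30 |
| 0/4 | 20/62 vs 6/57 | 21.7 | +5.9 | (6/51)/(20/42) = 0.25 |

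If each removed event is equally likely to come from either arm, the three middle rows cover 14/16 = 87.5% of cases and the extreme rows 1/16 each. Half the SE is 3.8 points, so the extreme splits exceed it. With six removed, near the top of the assumed range, a 5/1 split gives 15/57 − 9/60 = 11.3 points (shift −4.5) and a 1/5 split gives 19/61 − 5/56 = 22.2 points (shift +6.4).

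**5. When the distortion is small.** If the same share of events is lost in each arm, both odds are multiplied by the same factor and the odds ratio does not change. At the design rates it stays at 0.405. The distortion in the odds ratio comes from imbalance.

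The rule also removes event-free early leavers. Their number cannot be derived from the documents and is left out here.

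**The case against.** The strongest reply has four parts.

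- **More than one analysis is promised.** A reader might infer that the exclusion is the SAP's only commitment on missing data. The documents do not support that: the Missing Data section speaks of analyses in the plural, and this one is an example. It is, however, the only one named, and the optional COVID-19 list does not make up the difference.
- **Death may count as complete follow-up.** A reader might infer that early deaths are certain to be dropped. That goes beyond the text, because the term is undefined and the stated aim concerns missing data, which a known death is not. This part of the reply stands. It does not rescue early leavers with a qualifying FVC. Protocol 7.1.2 continues vital-status follow-up after withdrawal from procedures, where possible, but only to the call 28 days after the last dose. Written withdrawal of consent ends vital-status assessments (Protocol 5.3.4).
- **The exclusion has some use.** It removes the values carried forward longest, which is worth seeing. That stands, but it is a different purpose from testing alternative assumptions about unseen outcomes.
- **Little is at stake.** Protocol 10.4.2 reports secondary analyses of the primary endpoint as exploratory, and the SAP requires missing data and discontinuation reasons to be shown by arm. This stands and limits the severity.

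**Conclusion.** The point holds as a minor one. The only missing-data sensitivity analysis named in the SAP discards some observed primary events: early FVC declines followed by withdrawal and, if follow-up means time on study, early deaths. It leaves departures from missing at random untested.

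In the illustration, losing four such events moves the difference by −4.7 to +5.9 points over all splits, or −2.1 to +3.2 for splits from 3/1 to 1/3. The direction depends on which arm loses more. The event counts, mortality, splits and number removed are all assumptions, so these figures show what can happen and do not bound the effect. In particular, the documents do not support a claim that the shift stays under half a standard error.

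A reader might also infer that the trial's main result is biased. It is not affected by this rule: the primary ITT analysis keeps all randomized participants and the time-to-event analysis uses all follow-up. The harm is confined to one supplementary analysis.

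**What to change.** In the SAP's Missing Data section, replace the exclusion sentence with the following text, or add it as the main missing-data sensitivity analysis:

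> All randomized participants are retained. Every on-study death counts as an event, as does every participant without a Week-52 FVC whose last on-study FVC already meets the decline criterion of the primary endpoint. Observed Week-52 values are used where available. For other participants alive without a Week-52 FVC, Week-52 percent predicted FVC is multiply imputed within arm from baseline and all observed FVC under missing at random. Arm-specific delta shifts, over a range fixed before unblinding, are then applied to find the tipping point.

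The section should also state that fixing already-observed FVC declines as events, rather than imputing those participants, can only add events among leavers. It should say how transplant recipients enter this analysis.

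If the six-month exclusion is kept as well, define follow-up, report by arm how many observed events it removes, and label the result descriptive. Do not limit the exclusion to event-free participants, because that selects directly on the outcome. For example, removing six event-free pirfenidone participants alone would raise that arm from 10/61 = 16.4% to 10/55 = 18.2%.

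The cost is a short paragraph and a small amount of extra programming. No new data are needed.

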### **Time-to-event missing data**

In the analyses of the time-to-event endpoints, missing or incomplete data will be managed by censoring at the last date recorded without the event. In the case of partially missing dates, the following imputation will be done:

1. If day is missing, then imputed day will be the 15th of the month.
2. If day and month are missing, they will be imputed by inference from the participant's other visit dates.
3. If year is missing, it will be imputed by inference from participant's other visit dates.

## **Interim Analyses and Data Monitoring**

This phase II clinical trial was not designed to stop early for efficacy in order to preserve the 5% probability of a Type I error for the final analysis. Throughout the study, an external Data Safety Monitoring Board (DSMB) reviewed safety and administrative data periodically, according to the schedule specified in the DSMB Charter, to determine the safety and feasibility of continuing the trial. Open session reports summarized the following types of data: accrual, protocol deviations, data completeness, demographics and baseline characteristics, clinical and laboratory data, adverse events and other safety parameters, treatment compliance and dose modifications, reasons for treatment discontinuations, and causes of death. The open report included analyses with all participants combined (i.e., pooled across treatment group). The closed report presented the data according to treatment group in a blinded fashion. The DSMB could request additional participant-level data and/or recommend that the study stop temporarily or permanently for safety concerns that are set forth in the DSMB Charter, or for administrative reasons such as slow accrual. An interim DSMB meeting was convened on June 1, 2020 that focussed on the ongoing COVID-19 pandemic, and the potential permanent discontinuation of enrolment.

## **Scope of Adaptations**

Serious safety concerns could lead to a Data Safety Monitoring Board (DSMB) recommendation to temporarily stop the trial pending additional information, or to permanently stop the trial. Issues with

slow accrual could lead to a recommendation to stop the trial or to expand recruitment with marketing efforts and/or by adding centers, for example. The unprecedented COVID-19 pandemic precipitated the permanent discontinuation of enrolment.

### **Practical Measures to Minimize Bias**

Any level of unblinding, either of individual participants or of treatment estimates, could induce biases. Therefore, all study personnel were blinded throughout the study, seeing only pooled summaries, with the exception of the Data Coordinating Center (DCC) statisticians producing the DSMB closed reports and the Clinical Coordinating Center (CCC) statisticians producing the final analysis after the data lock. To minimize bias during the trial before the data lock, the treatment arms had masked labels such as “A” and “B.” Individual participant treatment assignments were not known unless there was a safety concern where knowledge of treatment assignment determined patient care.

### **Plan for Interim and Final Analyses, and Documentation**

- The DCC statisticians will perform interim analyses for DSMB periodic reports
- The DCC statisticians and the DSMB members will see the DSMB analyses broken down by masked treatment arm
- A decision to stop or modify the trial will be provided to the sponsor and investigators
- The CCC statisticians will perform final analyses.

Snapshots of the data available at each interim analysis will be preserved, as will all documentation of analysis plans, programming code and reporting provided at each interim.

### **Multiple Testing**

As this is a Phase II trial with only one single pre-specified primary endpoint, adjustment for multiple testing in the analyses is not planned for the primary endpoint or for the hypothesis-generating

secondary endpoints. In the exploration of the pre-specified subgroups, estimates of effect and 95% confidence intervals will be reported with an accompanying statement regarding multiplicity and the exploratory nature of the subgroup analyses.

## **Summary of Study Data**

All continuous variables will be summarized using the following descriptive statistics: n (non-missing sample size), mean, standard deviation, median, minimum, and maximum. The frequency and percentages (based on participants' non-missing values for each particular variable) of observed levels will be reported for all categorical measures. In general, all data will be listed, treatment, and participant, and when appropriate by visit number within participant. Age will additionally be summarized by pre-specified age groups. Selected other continuous variables, that are specified before the database lock, will be additionally summarized using categories.

All summary tables will be structured with a column for each treatment in the order (Placebo, Pirfenidone) and will be annotated with the total population size relevant to that table/treatment. The number of missing observations will be reported.

Summary tables of baseline characteristics will be based on the ITT population. Summary tables of adverse events will be based on the As Treated population. Summary tables of outcomes will be presented for the ITT population, with the primary endpoint also being presented using the Per Protocol population.

## **Subject Disposition**

Please refer to the accompanying spreadsheet for forms and variable names (TRAIL1 endpoints and dataset variable names.xlsx, Subject Disposition tab.)

The consort diagram will be presented.

<http://www.consort-statement.org/consort-statement/flow-diagram>

The number of participants reaching the milestones in the trial will show the number screened, randomized, and reaching each visit, or study close, and the number dropped out and for what reasons (death, toxicity, treatment failure, withdrew consent). A crosstabulation will show the accrual by quarter and by network and center. A listing of participant discontinuation from study medication will be presented for all randomized participants. Frequency counts and percentages of all participants providing informed consent, randomized/enrolled, completing and discontinuing from the study and study treatment will be presented according to treatment arm and overall. A summary of discontinuations will also be presented by visit. The proportion who discontinued the study early will be compared using chi-square test in the ITT population. The proportion who stopped treatment early on each arm will be compared using chi-square test in the as-treated population.

